4.3 Withdrawal Criteria

A patient may prematurely discontinue study drug and/or withdraw from the study at any time. A distinction must be made between premature discontinuation of study drug and withdrawal from the study. A patient may prematurely discontinue study drug and still continue his/her participation in the study.

The reasons for premature discontinuation of study drug and for withdrawal from the study must be documented in the eCRF. Reasons for premature discontinuation of study drug include, but are not limited to, the following:

- Withdrawal of consent/assent;
- Any event, laboratory abnormality, intercurrent illness, or other medical condition that indicates to the Investigator that continued participation is not in the best interest of the patient;
- Pregnancy;
- Patient failure to comply with Protocol requirements or study-related procedures;
- Termination of the study by the Sponsor or regulatory authority;

- Initiation of medications known to be potent CYP3A4 inhibitors (itraconazole, lopinavir/ritonavir, telaprevir, clarithromycin, ritonavir, ketoconazole, indinavir/ritonavir, conivaptan, and voriconazole), potent CYP3A4 inducers (avasimibe, carbamazepine, enzalutamide, mitotane, nevirapine, phenobarbital, phenytoin, rifabutin, rifampicin, rifapentine, and St John's wort), or potent UGT1A9 inhibitors and inducers (mefenamic acid and rifampicin);
- The patient experiences mean QT prolongation (mean QTcF interval >500 milliseconds AND increase by >60 milliseconds over the mean baseline QTcF);
- Severe allergic reactions to the study drug;
- The patient has CTCAE Grade ≥ 2 anemia AND the retest absolute reticulocyte count is below 50% of the baseline value. In this case, study drug will not be resumed and will be permanently discontinued; or
- The patient has suspected DILI meeting [Criterion 3](#) in [Appendix C](#).

Unless a patient withdraws his/her consent/assent to participate in the study, all patients should be encouraged to complete the remaining study visits, regardless of whether they are still receiving study drug.

For patients who are withdrawn from the study prior to completion of Study Visit 8, the Early Termination Visit procedures will be completed, if possible, at the time the decision is made to withdraw the patient. The Early Termination Visit will consist of all of the Study Visit 8 procedures. The reason for patient withdrawal must be documented in the eCRF.

In the case of a patient lost to follow-up, at least 3 attempts to contact the patient must be made and documented in the patient's records.

Withdrawn patients may be replaced, unless a patient is withdrawn for a reason related to safety, as per the judgment of the Investigator. A maximum of 20 patients will be randomized for the study.

4.4 Screen Failures and Patient Re-Screening Procedures

Patients who sign consent/assent but do not meet all of the eligibility requirements defined in [Sections 4.1](#) and [4.2](#) and therefore are not randomized will be considered a screen failure. Screen failure patients may be re-screened for the study if approval is given by the Medical Monitor. All re-screened patients must be re-consented and sign a new Informed Consent Form (ICF)/assent prior to completion of any re-screening study procedures.

Re-screened patients will be assigned a new patient number at the time of re-screening. The re-screened patient's new eCRF casebook will contain a reference to the patient's previous identification number.

5 STUDY TREATMENTS

5.1 Treatment Groups

5.1.1 Setanaxib

Patients will receive the following setanaxib doses according to age at the time of consent/assent:

- For patients aged 12 to 17 years: 1200 mg/day (800 mg morning + 400 mg evening) for 24 weeks; and
- For patients aged ≥ 18 years: 1600 mg/day (800 mg BID) for 24 weeks.

5.1.2 Placebo

Matching film-coated placebo tablets, containing only excipients, will also be provided.

5.2 Background Therapy

Throughout the study, all patients will remain on their maximum allowed dose or maximum-tolerated daily dose of RAS blockade using ACEi and/or ARB. Patients with proven intolerance to ACEi and ARB are allowed in the study. No clinically significant PK drug-drug interactions are expected to arise from combining setanaxib with ACE inhibitors.²⁷ Similarly, setanaxib is not expected to affect the PK of ARBs, with the possible exception for products that are substrates of CYP2C9 (losartan, irbesartan, azilsartan); setanaxib increased the losartan maximum plasma concentration (C_{max}) and area under the concentration-time curve (AUC) by 70% and 45%, respectively; this effect may not be clinically significant. No clinically significant interactions are expected with valsartan, telmisartan, olmesartan, candesartan, or eprosartan.²⁸

5.3 Dose Justification

The adult dosing regimen for this study is the highest dose level of setanaxib previously investigated and considered safe and well tolerated, ie, 800 mg BID (1600 mg/day). At the adult dose level of 800 mg BID, the expected exposures are similar to the defined NOAEL in the preclinical setting for both the parent drug (setanaxib) and its active metabolite (GKT138184). The NOAEL-defining toxicology signals have been monitored in the clinical setting and no safety signals related to those findings have been observed in either healthy subjects at 800 mg BID for 10 days or in adult patients at up to 800 mg BID for up to 76 weeks.

In the completed clinical study GSN000300, 111 patients with PBC were randomized 1:1:1 to receive placebo, setanaxib 400 mg once daily, or setanaxib 400 mg BID for 24 weeks. This dosing regimen was considered safe and well tolerated, and the treatment was pharmacologically active (based on observed dose-related improvements in liver enzymes); however, the observed clinical efficacy in the target patient population was considered insufficient. As a result, doses of up to 800 mg BID are being used in the ongoing Phase 2b/3 study in patients with PBC and elevated liver stiffness (GSN000350) and in the Phase 2 study in patients with recurrent or metastatic SCCHN (GSN000400). The safety data from the ongoing clinical studies are regularly reviewed by the Sponsor Safety Management Team (blinded safety information) and by the respective study IDMCs (unblinded review). To date, there have not been any safety or tolerability concerns and both studies have continued without interruption. In the ongoing, blinded Phase 2b/3 study in PBC patients (GSN000350), 4 cases of increased hepatic enzymes (ie, suspected DILI) have been

observed to date in these patients with chronic liver disease. The patients were asymptomatic at the time of the suspected DILI. All cases have resolved. To date, no suspected DILI events have been reported in any of the other completed or ongoing clinical studies. The same 800 mg BID adult dose level is selected for the current study in Alport syndrome with the intent to be both safe and tolerable, and to provide an assessment of preliminary clinical efficacy.

The relationship between dose and inhibition of NOX1 and NOX4 pathways in humans is not clearly established, but estimates based on preclinical in vitro experiments and human PK suggest that at a dose of setanaxib of 800 mg BID, the average target inhibition over the dosing interval is about 80%. This is superior to the 400 mg BID dose level (about 68% inhibition). These estimates suggest that the 800 mg BID dosing regimen may provide sufficient target inhibition to evaluate the mechanism of action and clinical effects of setanaxib.

The dose selection for the adolescent patients is based on results from completed and ongoing studies, indicating that a dose of setanaxib of 800 mg BID in adults is safe, well tolerated, and may provide clinical benefit in adult patients. Since there is no suggestion that the pharmacology^{29,30,31,32} or safety and tolerability of setanaxib will be different in adolescent patients with Alport syndrome, the dose selection for adolescent patients aims to achieve the same systemic exposure levels as those seen in adults following dosing at the 800 mg BID dose level.

Available data for setanaxib suggest a drug disposition profile where renal clearance of unchanged parent drug represents a negligible portion of the elimination and where metabolism via UGT1A9-mediated glucuronidation and CYP3A4 are the dominant elimination pathways, with only minor contributions from other elimination pathways.

Following allometric principles, a dose level of 1200 mg/day (800 mg morning + 400 mg evening) for the 12 to 17 years of age range (restricted to a body weight of at least 40 kg) has been selected. On average, a 40 kg patient at 1200 mg/day is expected to have approximately 14% higher exposure (AUC) than a 70 kg patient at 1600 mg/day.

5.4 Randomization and Blinding

This is a randomized, double-blind study. Patients meeting eligibility criteria will be randomized in a 2:1 ratio to receive either setanaxib or placebo and the randomization of patients will be managed by an Interactive Response Technology (IRT) system. To ensure balance among treatment groups, randomization will be stratified by age group (12 to 17 years of age and ≥18 years of age) at the time of consent/assent.

After confirming all eligibility criteria (including laboratory values from Study Visits 1 and 2, UPCR, and eGFR), randomization will be performed through IRT, which will trigger the first shipment of study drug to the site for the patient. The patient does not need to be on site at the time of randomization. Study Visit 3 should occur within 10 days (+3 days) after randomization. Following the initial shipment, there will be an automatic resupply of study drug to the site for dispensing to the patient at Study Visits 5, 6, and 7.

Patients will be assigned a treatment assignment as determined by the IRT system. The IRT system will manage all aspects of treatment and logistical aspects of study product supply.

Randomized patients who prematurely discontinue the study for non-safety reasons may be replaced. Data should be continuously collected until Week 24, if possible.

5.5 Breaking the Blind

Individual treatment assignments may be unblinded when immediate knowledge of the treatment assignment is needed to optimize the clinical management of the patient. In case of medical emergency, the Investigator will have direct access to unblinding of treatment. In such emergency situations, the responsibility to break the treatment code resides solely with the Investigator. The Investigator should contact the Medical Monitor as soon as possible to discuss the event. The IRT system allows for immediate emergency unblinding of a patient by the site when determined necessary. Site personnel will be trained by the Clinical Research Associate (CRA) on the unblinding procedures.

A sealed code break envelope will be prepared and provided to the study site to enable emergency code break for an individual patient.

Documentation of the blind break, including the patient's identification, reason for breaking the blind, and the date and time of breaking the blind, must be retained in the patient's source notes at the site in such a way as to avoid unblinding the treatment assignment to other site or Sponsor blinded personnel.

5.6 Drug Supplies

5.6.1 Formulation and Packaging

Setanaxib film-coated tablets contain 400 mg setanaxib formulated with excipients and will be provided in high-density polyethylene (HDPE) bottles.

Matching film-coated placebo tablets, containing only excipients, will also be provided in HDPE bottles.

5.6.2 Study Drug Preparation and Dispensing

Study drug will be dispensed at visits specified in [Appendix A](#), following IRT procedures and study drug assignment.

5.6.3 Study Drug Administration

When study drug is dispensed, the patient will be instructed on study drug administration.

Patients must take the first dose of study drug in the presence of site staff during Study Visit 3. Similarly, the morning dose at the Week 2, Week 12, and Week 24 visits should be taken at the study site, to allow for proper PK sampling. Fasting prior to PK sampling will not be required.

Patients will self-administer (with caregiver supervision, as needed, if the patient is 12 to 17 years of age) 2 tablets of blinded study drug (setanaxib or placebo) in the morning and either 1 or 2 tablets of blinded study drug in the evening (according to age) with food or up to 30 minutes after eating a meal. Tablets may be divided (preferably using a pill cutter) if needed for easier administration. If divided, care must be taken to make sure that the whole dose is ingested, and tablets should be divided immediately prior to dosing, without any storage after being cut.

5.6.4 Treatment Compliance

Patients will be instructed to return all empty bottles and unused study drug to the site at the study visits indicated in [Appendix A](#). Patients will return all remaining unused study drug at Study

Visit 8. Treatment compliance will be assessed at each study visit after baseline (Day 1) through Week 24.

Accountability of the used and unused study drug will be recorded. Compliance with the study drug regimen will be evaluated by counting unused tablets. During the Treatment Period, if compliance is not between 80% and 120%, inclusive, the patient will be counseled about the importance of compliance with the study drug regimen.

5.6.5 Storage and Accountability

Setanaxib formulations should be stored at room temperature (15°C to 25°C [59°F to 77°F]) and should not be frozen.

The Investigator or designee will maintain accurate records of receipt and condition of study drug. Any reasons for departure from the Protocol-specified dispensing regimen must also be recorded. All unused study drug for all patients should be maintained until review by a study monitor during site visits and at the time of database lock. The site will maintain accountability records to document receipt and dispensing of setanaxib and placebo throughout the study.

All unused setanaxib and placebo tablets remaining at the completion of the study will either be returned to the Sponsor or destroyed at the study site, per Sponsor instruction. It is the responsibility of the Investigator to ensure that the Sponsor has provided written authorization prior to return or destruction of study drug. Study drug return/destruction will be documented in the site files. No unused study drug may be disposed of until fully accounted for by the study monitor.

Refer to the Pharmacy Manual for additional details.

5.7 Prior and Concomitant Medications and/or Procedures

5.7.1 Excluded Medications and/or Procedures

The following medications and/or procedures will exclude patients from participation in this study:

- Medications known to be potent CYP3A4 inhibitors (itraconazole, lopinavir/ritonavir, telaprevir, clarithromycin, ritonavir, ketoconazole, indinavir/ritonavir, conivaptan, and voriconazole), potent CYP3A4 inducers (avasimibe, carbamazepine, enzalutamide, mitotane, nevirapine, phenobarbital, phenytoin, rifabutin, rifampicin, rifapentine, and St John's wort), or potent UGT1A9 inhibitors and inducers (mefenamic acid and rifampicin) within 21 days prior to study drug administration;
- Systemic steroids given for a period of greater than 2 weeks are not permitted;
- Investigational agents within 12 weeks of signing informed consent/assent or 5 half-lives of the investigational agent (if known), whichever is longer;
- Prior treatment with setanaxib; and
- Any surgery (eg, gastric bypass) that might significantly affect absorption of medicines (as judged by the Investigator).

5.7.2 Medications to be Used With Caution

Setanaxib has been shown to be a weak inhibitor of OAT3, CYP2C9, and CYP2C19 in a clinical pharmacology study. In addition, setanaxib inhibited BCRP and P-glycoprotein in vitro. This may result in increased exposures of applicable concomitant medications, and hence caution should be exercised with use of the following:

- Medications that are primarily eliminated through OAT3;
- Sensitive CYP2C9 and CYP2C19 substrates that have a narrow therapeutic range, such as warfarin and phenytoin (CYP2C9) and S-mephenytoin (CYP2C19); and
- Sensitive substrates of BCRP and P-glycoprotein, such as digoxin.

In vitro data suggest that setanaxib is an inducer of CYP2B6. This may result in decreased exposures and therefore reduced efficacy of applicable concomitant medications, and hence caution should be exercised with use of the following:

- Sensitive CYP2B6 substrates, such as tamoxifen, valproic acid, and cyclophosphamide.

5.7.3 Allowed Medications

All patients must be receiving the maximum allowed dose or maximum-tolerated daily dose of an ACEi and/or ARB that has been stable for at least 8 weeks prior to consent/assent. A stable dose is defined as a dose within 25% of the dose at randomization. Patients with proven intolerance to ACEi and ARB are allowed in the study.

SGLT2 inhibitors are allowed provided they have been given at the same dose for at least 8 weeks prior to Screening and are given at the same dose during the study.

Local and topical steroids are permitted.

Patients on stable methadone or buprenorphine maintenance treatment for at least 6 months prior to Screening Visit 1 may be included in the study. Medicinal cannabis and cannabidiol products are not exclusionary and may be allowed if the prescription and diagnosis are reviewed and approved by the Investigator.

5.7.4 Documentation of Prior and Concomitant Medication Use

Medications taken within 3 months prior to the date of consent/assent and concomitant medications and therapies administered throughout the course of the study until the last patient visit will be recorded in the eCRFs.

6 STUDY PROCEDURES

Study procedures will follow the Schedule of Procedures ([Appendix A](#)).

7 EFFICACY ASSESSMENTS

7.1 Pharmacokinetic Sampling

PK samples will be collected at timepoints specified in [Appendix A](#).

PK samples will be collected at Week 2 (pre-dose and 1, 2, 3, 4, and 6 hours post-dose), at Week 12 (pre-dose), and at Week 24 (pre-dose).

The PK sampling windows are as follows:

- Pre-dose: within 90 minutes prior to dose;
- 1, 2, 3, and 4 hours post-dose: ± 5 minutes; and
- 6 hours post-dose: ± 15 minutes.

7.2 24-Hour Urine Testing

Urine testing will be performed at visits specified in Appendix A. Urine testing results will include creatinine clearance, total albumin, total cortisol, total creatinine, total protein, and UPCR, based on a 24-hour sample collection at each specified timepoint.

The screening urine collection consists of 2 separate 24-hour collections. Patients will be provided with containers for collection and will collect urine at home on 2 occasions at least 2 weeks apart prior to returning to Visit 2. The urine collection is to be kept in the fridge and must be provided to the site within 48 hours of completing each 24-hour collection. UPCR will be determined for 24-hour urine collections during the Screening Period to confirm eligibility. The geometric mean values will be used for baseline.

During the study visits prior to Weeks 6, 12, 24 (or Early Termination), and the Follow-up Visit, the patient will be provided with containers for urine collection. One 24-hour urine collection is to be done by the patient at home within 5 days prior to Visit 5 (Week 6), Visit 6 (Week 12), and the Follow-up Visit, respectively. Prior to the End of Study Visit at Week 24 (or Early Termination), urine will be collected on 2 occasions at least 1 week apart and not more than 2 weeks apart, with the last one completed within 5 days prior to the study visit. UPCR geometric mean values will be used for the final analysis. The urine collection must be kept in the fridge and is to be provided to the site within 48 hours of completing each 24-hour collection.

A urine collection may need to be repeated if it is deemed potentially inadequate, as per the evaluation of the testing parameters by the Medical Monitoring team. For rare occasions where a 24-hour collection is not feasible for an adolescent study patient, an alternative method for urine collection may be accepted (such as a 12-hour sample), if discussed and pre-approved by the Medical Monitoring team.

UPCR history up to 12 months prior to signing informed consent/assent, including local laboratory results, will be collected.

7.3 Estimated Glomerular Filtration Rate

Plasma samples for eGFR will be collected at timepoints specified in Appendix A.

The central laboratory will calculate the eGFR using the CKD-EPI formula for patients ≥ 18 years of age and the revised bedside Schwartz formula for patients 12 to 17 years of age.

Note: Two eGFR samples will be collected at Week 24, at least 1 week apart but no more than 2 weeks apart, with the last sample collected during the Week 24 study visit.

eGFR history up to 12 months prior to signing informed consent/assent, including local laboratory results, will be collected.

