3.1.3 Planned Number of Patients

The study is planned to enroll and treat approximately 18 patients. Up to 6 patients should be in the age group of 12 to 17 years old at the time of consent/assent, and a minimum of 12 patients should be ≥ 18 years of age. In the EU, only adult patients (18 to 50 years, inclusive) will be

enrolled. To ensure balance among treatment groups, randomization will be stratified by age group (12 to 17 years of age and ≥ 18 years of age) at the time of consent/assent.

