APPENDIX B: CLINICAL LABORATORY ANALYTES

Standard Safety Chemistry Panel

Alanine aminotransferase	Albumin
Alkaline phosphatase	Amylase
Aspartate aminotransferase	Bicarbonate
Blood urea nitrogen	Calcium
Chloride	Creatine kinase
	Estimated glomerular filtration rate (eGFR)
Creatinine	[1]
Gamma-glutamyl transferase	Glucose
Inorganic phosphorus	Lactate dehydrogenase
Lipase	Potassium
Sodium	Total bilirubin
Total protein	Uric acid

1. Calculated by the central laboratory using the Chronic Kidney Disease Epidemiology Collaboration (CKD-EPI) formula for patients ≥ 18 years of age and the revised bedside Schwartz formula for patients 12 to 17 years of age:

$$eGFR = 141 \times \min(SCr/K, 1)^{\alpha} \times \max(SCr/K, 1)^{-1.209} \times 0.993^{Age} \times 1.018[\text{if female}] \times 1.159[\text{if black}]$$
where SCr is standardized serum creatinine in mg/dL, K is 0.7 for females and 0.9 for males, α is -0.329 for females and -0.411 for males, min indicates the minimum of SCr/K or 1, and max indicates the maximum of SCr/K or 1).
Reference: Levey AS, Stevens LA, Schmid CH, et al. A new equation to estimate glomerular filtration rate. *Ann Intern Med.* 2009;150(9):604-612.
Bedside Schwartz formula = $([0.413 \times \text{height (cm)}] / \text{Scr [mg/dL]})$.

Serology

Hepatitis B virus	Hepatitis C virus
Human immunodeficiency virus	

Coagulation

International normalized ratio (INR) [1]

1. INR testing is to be completed as part of Screening assessments only (Visit 1 or Visit 2). Thereafter, INR will be tested as part of follow-up assessments for a suspected case of drug-induced liver injury (DILI). See [Appendix C](#) for details regarding additional follow-up assessments to be completed for suspected cases of DILI.

Endocrinology

Follicle-stimulating hormone (FSH) [1]	Human chorionic gonadotropin [2]
Thyroid-stimulating hormone	Thyroxine (T4)

1. In female patients who are not using hormonal contraception or hormonal replacement therapy but with suspected menopause and less than 12 months of amenorrhea, a high FSH level in the postmenopausal range will be required at Screening to confirm a postmenopausal state.
2. For women of childbearing potential only. A serum pregnancy test will be performed at Study Visit 2. A pregnancy test via a local urine assessment will be performed at all other applicable study visits prior to study drug dosing.

Hematology

Hematocrit

Platelets

Reticulocyte count

Hemoglobin

Red blood cell count

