In the analysis phase, the ratio of eGFR at 24 weeks compared to baseline will be calculated for each patient within each imputed dataset. The ratio of eGFR of the log-transformed data will be analysed using Robust Regression with independent variables of treatment and log-transformed baseline eGFR. M-estimation will be used with Huber weights. Sample SAS code below:

```
*****
** TRT = treatment group
** CHG = Change of log-eGFR baseline ratio at 24 weeks
** BASE = log-baseline eGFR
*****

proc robustreg data=chg method=m (wf=huber) outest=chg1 covout;
  by _imputation_;
  class TRT;
  model CHG = BASE TRT;
run;
```

Pooling phase

In the pooling phase, the results from these 25 analyses will be combined using Rubin's method to construct the treatment estimate using the parameter estimates and associated standard errors. Sample SAS code below:

```
proc mianalyze data=chg1;
  modeleffects estimate;
  stderr stderr;
  ods output ParameterEstimates=est2;
run;
```

If the multiple imputation approach is such that the model convergence is questionable and the given parameter estimates cannot be obtained, then the ratio of eGFR at 24 weeks compared to baseline will be evaluated using similar MMRM model as for UPCR, otherwise, MMRM analysis will be considered as sensitivity analysis.

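### No date is given at which age selects the eGFR formula, so a patient who turns 18 on study could switch formula and show a spurious rise in the Week 24/baseline ratio

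*Protocol*

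**What the plan says.** Protocol 7.3 states the rule: the central laboratory uses CKD-EPI for patients aged 18 or older and "the revised bedside Schwartz formula for patients 12 to 17 years of age". The synopsis, the study design summary (3.1), inclusion criterion 9, the Schedule of Procedures footnote and Appendix B repeat it. None gives a reference date for age.

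Elsewhere the protocol does give one. For dose, 5.1.1 says "Patients will receive the following setanaxib doses according to age at the time of consent/assent". For allocation, 5.4 says "randomization will be stratified by age group (12 to 17 years of age and ≥18 years of age) at the time of consent/assent". The age categories in SAP 3.3.4 are also taken at consent.

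The endpoint is a within-patient ratio. Under SAP 3.5.2, "the ratio of eGFR at 24 weeks compared to baseline will be calculated for each patient within each imputed dataset", and baseline and Week 24 are each the geometric mean of two assessments. The SAP does not fix one formula per patient, does not call for recalculation, and has no sensitivity analysis for a patient who reaches 18 during the study.

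**The concern.** CKD-EPI and bedside Schwartz are different equations and need not agree for the same person on the same day. In a ratio of Week 24 to baseline, a change of equation between numerator and denominator looks like a change in kidney function. A birthday between the two screening samples would instead mix the equations within the baseline.

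The arms have about 12 and 6 patients, so one such patient carries weight in an estimate meant to guide the next studies. The mixed values would also enter the imputation models, which use eGFR from every visit.

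**Working it through.** The plan gives no figure for a change of formula, so there is none to reproduce.

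**Formulas (Protocol Appendix B).**
- Schwartz = 0.413 × height (cm) / SCr (mg/dL).
- CKD-EPI = 141 × min(SCr/K, 1)^α × max(SCr/K, 1)^-1.209 × 0.993^Age × 1.018 if female, where "K is 0.7 for females and 0.9 for males, α is -0.329 for females and -0.411 for males".

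Heights and creatinine values below are assumptions. The race factor of 1.159 is left out; where it applied, it would multiply the post-switch value by a further 1.159.

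**Jump at age 18 with unchanged creatinine.**

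| Patient | Schwartz | CKD-EPI | Ratio |
|---|---|---|---|
| Boy, 175 cm, SCr 1.0 | 0.413 × 175 / 1.0 = 72.3 | 141 × (1/0.9)^-1.209 × 0.993^18 = 109.4 | 1.51 |
| Boy, 165 cm, SCr 0.9 | 75.7 | 124.3 | 1.64 |
| Boy, 175 cm, SCr 2.41 | 30.0 | 37.8 | 1.26 |
| Girl, 160 cm, SCr 1.0 | 66.1 | 82.2 | 1.24 |
| Girl, 150 cm, SCr 0.7 | 88.5 | 126.5 | 1.43 |
| Girl, 165 cm, SCr 2.0 | 34.1 | 35.5 | 1.04 |

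On a grid of Schwartz eGFR from 30 (the entry floor) to 120, the jump is:
- boys 160-190 cm: +14% to +69%, median +39%;
- girls 150-180 cm: -8% to +43%, median +19%, with 4% of the grid below zero.

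Setting aside the extremes of height, about 25-65% for boys and about 0-40% for girls is a fair summary. The girls' jump is smallest at low eGFR.

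**Partial switches.** If only one of the two Week 24 samples follows the birthday, the log effect is halved: √1.51 = 1.23, or +23% instead of +51%. A birthday between the two screening samples also halves it.

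**Chance of a switch.** Protocol 3.1.3: "Up to 6 patients should be in the age group of 12 to 17 years old at the time of consent/assent". Assume ages uniform over the six years 12-17. The exposed time is 24 weeks, or about 29.5 weeks with 4 weeks of screening and up to 10 days from randomization to Visit 3. Per adolescent, p = (1/6) × 24/52 = 0.077 to (1/6) × 29.5/52 = 0.095. The chance of at least one switch among n adolescents is 1 - (1 - p)^n:
- n = 2: 15% to 18%;
- n = 3: 21% to 26%;
- n = 6: 38% to 45%.

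**Effect on the treatment comparison.** Take one patient with a log jump of 0.40 (ratio e^0.40 = 1.49), arms of 12 and 6, and an assumed log-change SD of 0.10. The SE of the difference is 0.10 × √(1/12 + 1/6) = 0.05.
- MMRM (no down-weighting, complete data): +0.40/12 = +0.033 if the patient is on setanaxib, -0.40/6 = -0.067 if on placebo.
- Huber M-estimation with log baseline as covariate, by simulation: about +0.015 on setanaxib (0.3 SE) and about -0.033 on placebo (0.7 SE).

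**With one formula per patient.** The artefact is zero under Schwartz apart from true growth. Under CKD-EPI throughout, only the age term moves: 0.993^0.5 = 0.996 over half a year.

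**The case against.** The documents do not say that current age decides the formula; they are silent. They also use the 12-17 and 18-or-older labels elsewhere without repeating the consent anchor: the evening tablet count in Protocol 5.6.3 and the compliance multiplier in SAP 3.3.7 plainly mean the dose group set at consent. The eGFR rule could be read the same way, and laboratory or programming specifications outside these documents may settle it. This stands, so the size of the effect is conditional. Age at sampling is still the more natural reading, because CKD-EPI contains age as a term and the laboratory needs an age for each sample.

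Exposure is limited. Six is a cap with no minimum, and EU sites enrol adults only. The main eGFR analysis uses Huber weights because outliers are expected, and no formal testing is planned. All of this stands. Huber weighting reduces the shift but does not remove it, and the MMRM that serves as fallback or sensitivity analysis does not reduce it.

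A reader might go further and infer that the jump exceeds any plausible drug effect. The documents state no expected eGFR effect, so that cannot be shown. A reader might also infer that a real decline would be hidden from safety review. Serum creatinine, BUN, 24-hour creatinine clearance and cystatin-C are all collected and do not depend on the eGFR formula.

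**Conclusion.** The gap is real and should be fixed, but it does not threaten the trial. Followed by age at sampling, the rule puts a spurious rise into a named secondary endpoint for any patient whose 18th birthday falls on study, except some girls with low eGFR, in whom the change is close to zero. Most likely zero or one patient is affected. If one is, the shift in the treatment comparison is about 0.3 to 0.7 of a standard error in the Huber analysis and 0.7 to 1.3 in MMRM.

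These sizes rest on the assumed heights and creatinine, uniform ages, a log-change SD of 0.10 that the documents do not give, and a laboratory that goes by age at sampling. The problem can be corrected from data already collected, so it is a should-fix and not a condition for running the study.

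**What to change.** In SAP 3.5.2, state that for the eGFR endpoint the formula is set by age at consent/assent and kept for all of that patient's visits. Where the laboratory has switched, recompute the affected values from the recorded creatinine and height before imputation. Make the same statement in Protocol 7.3 and Appendix B if the protocol is amended for other reasons.

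Decide this before unblinding; otherwise the handling of one outlying patient becomes a data-driven choice.

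The cost is a sentence or two and a short derivation. Creatinine is in the chemistry panel, and Protocol 8.12 collects height for everyone at Day 1 and Week 24. Height at the other eGFR visits is tied to the same undated 12-17 label, so the SAP should say that the nearest recorded height is used if one is missing after the birthday. No resampling is needed.
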